 - b. GCS 3–12 with GCS motor score =6 within 4 hours after injury AND documented intracranial abnormalities on imaging
 - c. GCS 13–15 within 4 hours after injury AND documented intracranial abnormalities on imaging
 - d. Loss of consciousness (LOC) > 30 min.
 - e. Post-traumatic amnesia (PTA) > 24 hours
- 8. Out of PTA at the time of enrollment (GOAT>75)
- Clinically significant depressive symptoms: meets criteria for Major Depressive Episode on the MINI or has a total score ≥ 23 on the Inventory of Depressive Symptomatology – Clinician rated (IDS-C)

Exclusion criteria:

- 1. Uncontrolled medical illness
- 2. Behavioral dyscontrol, defined as the presence of verbally or physically aggressive behavior in the past month, as evidenced in medical records, pre-screening interviews, or observed by any study staff
- 3. Presents with PTSD as the primary diagnosis, as determined by a clinician
- 4. Substance use disorder, moderate or severe, within the past 6 months
- 5. Has bipolar disorder, a primary psychotic disorder or current psychotic symptoms, or acute suicidality or homicidality
- 6. Currently receiving regular (≥ 2 times/mo.) psychosocial treatment for depression
- 7. Has participated in CBT for depression within the past 6 months
- 8. Individuals with history of dementia or severe cognitive impairment that is not related to TBI (e.g., cognitive impairment requiring assistance with basic activities of daily living, such as getting ready in the morning)

Recruitment: Subjects will be recruited through a number of sources. Spaulding Rehabilitation Hospital (SRH) will be the main recruitment site.

Outpatient Clinics

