of a meeting with a clinician for a structured diagnostic interview and assessment of depressive severity and neuropsychiatric symptoms, the completion of self-report questionnaires, and neuropsychological testing. This visit may be split into two parts, with the neuropsychological assessment occurring during the second part, in order to accommodate subjects' potential limitations due to fatigue.

In the first phase of recruitment, we will enroll 10 subjects in order to pilot test the newly developed manual in a nonrandomized, open trial. Based on objective and qualitative feedback from participants, the CBT-TBI manual, which includes materials such as CBT homework and study diaries, will then be revised.

Once the CBT-TBI manual has been revised, we will enroll up to 60 subjects in the second phase of recruitment with the goal of randomizing 40 participants. They will be enrolled using the same procedure as described in the open trial (N=10), but eligible participants will be randomly assigned in consecutive order to intervention or waitlist control group. Given that history of pre-injury MDD is the strongest predictor of post-TBI depression¹² and the higher incidence of MDD in women than in men,⁷³ randomization will be stratified by history of MDD and gender, so that both conditions include the same number of subjects with and without pre-injury MDD, as well as males and females. The randomization list will be provided by the biostatistician and maintained by the research staff. During the first 12 weeks, as per the schedule outlined below, participants randomly assigned to the waitlist control group will be seen only for assessments. Control arm participants will receive treatment as usual outside of our clinic and scheduled assessments in our clinic for 12 weeks. After 12 weeks, they will be offered the CBT-TBI treatment.

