Post Treatment Visit Assessment: A brief survey assessing the perceived helpfulness of the subject matter discussed at each treatment visit.

End of Treatment Assessment: A brief survey assessing the feasibility and perceived helpfulness of the intervention.

Other:

Epidemic – Pandemic Impacts Inventory (EPII)¹⁰⁸: a newly developed measure designed to learn about the impact of the coronavirus disease pandemic and future epidemics and pandemics on various domains of personal and family life.

All data will be entered directly into REDCap by the study clinicians and subjects. Completion of web-based, self-report measures via computer or tablet is likely to be more appealing to the study population who may experience physical injuries that impact writing abilities. Further, use of REDCap will likely minimize missing self-report study data and allow for immediate follow up on missing items, which is likely to be relevant for individuals who have sustained TBIs and frequently experience problems with attention and concentration. In the event that circumstances inhibit the ability to directly enter the data electronically (via computer or tablet), paper copies will be provided for clinician-rated or self-report administration. These paper copies will be directly downloaded from REDCap to ensure that the measures look identical to the electronic copies.

Table 1 below outlines the schedule of assessments for each phase of the study

Assessment	Screen	Wk 1	Wk 2	Wk 3	Wk 4	Wk 5	Wk 6	Wk 7	Wk 8	Wk 9	Wk 10	Wk 11	Wk 12 / Last Visit	3mo F/u
Informed Consent;	Х													
UBACC	37		-											
Inclusion/Exclusion Criteria	X													
Demographics/ Contact Information	Х													
Clinician Administered Psychiatric History Form	X													
OSU TBI Form	Х													
Release of Information	Х													
GOAT	Х													
MINI	Х													
C-SSRS	Х												Х	Х
AUDIT-C	Х													
Substance Use Questionnaire	Х													
Concomitant Treatment Log	Х		Х		Х		Х		Х		Х		Х	Х
Adverse Events			Х		Х		Х		Х		Х		Х	Х
CTAS	Х												Х	Х
IDS-C	Х												Х	Х
GOS-E	Х												Х	Х
QIDS-C			Х		Х		Х		Х		Х			
PROMIS Depression	Х		Х		Х		Х		Х		Х		Х	Х
BDI-II	Х	Х	Х	Х	Х	Х	Х	Х	Х	Х	Х	Х	Х	Х
HADS	Х												Х	Х
RPQ	Х						Х						Х	Х
Neuropsych Battery (see separate table for individual tests)	Х												Х	
Neuro-QOL Cognition Function – SF	Х												Х	Х

Table 1: Schedule of Assessments for Active CBT Patients

Anger-Affect Fixed	Х						Х						X	Х

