Form														
Neuro-QOL Ability to	Х						Х						Х	Х
Participate in Social														
Roles and Activities-SF														
Neuro-QOL Satisfaction	Х												Х	Х
with Social Roles and														
Activities-SF														
Neuro-QOL Emotional	Х												Х	Х
and Behavioral														
Dyscontrol-SF														
Coping Attitudes Scale	Х						Х						Х	Х
Awareness	Х												Х	
Questionnaire (patient)														
NIH Toolbox Meaning	Х						Х						Х	Х
and Purpose														
ATQ-R	Х						Х						Х	Х
Activity Tracker (data			Х	Х	Х	Х	Х	Х	Х	Х	Х	Х	Х	
syncs wirelessly)														
WAI-SF							Х						Х	
							(patient							
							version only)							
PROMIS Pain Intensity	X						X						X	X
PROMIS Pain	Х						Х						Х	Х
Interference														
Beck Hopelessness Scale	Х												Х	Х
STTS-R and interview													Х	
Post treatment		Х	Х	Х	Х	Х	Х	Х	Х	Х	Х	Х		
assessment (participant)														
Homework Compliance			Х	Х	Х	Х	Х	Х	Х	Х	Х	Х	Х	
(therapist)														
End of Treatment													Х	
Feedback														
COVID-19	Х												Х	Х
Supplemental Survey														
Approximate Time	240	< 10	30	< 10	30	< 10	45	< 10	30	< 10	30 min	< 10	180 min	60 min
Estimate	min	min	min	min	min	min	min	min	min	min		min		

Table 2. Schedule of Assessments for Waitlist Patients (note: after WL week 12 patients continue with Active CBT Assessments for 12 weeks)

Assessment	Screen	WL Wk 2	WL Wk 4	WLWk 6	WL Wk 8	WL Wk 10	WL Wk 12 / Last Visit
Informed Consent; UBACC	Х						
Inclusion/Exclusion Criteria	Х						
Demographics/ Contact Information	Х						
Clinician Administered Psychiatric History Form	X						
OSU TBI Form	Х						
Release of Information	Х						
GOAT	Х						
MINI	Х						
C-SSRS	Х						
AUDIT-C	Х						Х
Substance Use Questionnaire	X						
Concomitant Treatment Log	Х	X	X	X	Х	X	Х
Adverse Events		X	Х	X	X	X	Х
CTAS	Х						Х
IDS-C	Х						Х
GOS-E	Х						Х
QIDS-C		Х	Х	X	Х	Х	
PROMIS Depression	Х	Х	Х	X	Х	X	Х
BDI-II	Х						Х
HADS	Х						Х
RPQ	Х						Х
Neuropsych Battery (see separate table for individual tests)	Х						X

Neuro-QOL Cognition	Х						Х
Function – SF							
Anger-Affect Fixed	Х						Х
Form							
Neuro-QOL Ability to	Х						Х
Participate in Social							
Roles and Activities-SF							
Neuro-QOL Satisfaction	Х						X
with Social Roles and Activities-SF							
Neuro-QOL Emotional	Х						Х
and Behavioral							
Dyscontrol-SF							
Coping Attitudes Scale	Х						Х
Awareness	Х						Х
Questionnaire (patient)							

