External memory compensation s	• Such as notebooks and calendars	Memory impairment	Useful strategies for patients with TBI and memory problems, ¹²⁷ as well as adults with ADHD. ⁶⁹
Include support person (when possible)	Helps with treatment planning and carrying out homework assignments	Impaired insight Problems with generalization	Increased repetition/prompting likely to improve self-awareness, follow through and generalization of skills

VI. BIOSTATISTICAL ANALYSIS

Preliminary analyses will describe the participants' sociodemographic and clinical characteristics. Comparisons will be made using Mann-Whitney or chi-square tests to determine if the randomization provided a balanced sample and if patients who dropped out differ from those who did not. All analyses will be conducted using the SPSS and/or Stata statistical packages.

Aim 1 (Manual Development and Acceptability and Tolerability in Open Trial): We will use descriptive statistics to report the number of intervention sessions attended (we expect > 80%), number of assessment sessions attended (we expect > 80%), number of study completers (we expect > 80%), and rate of satisfaction with treatment (total STTS-R score).

Aim 2 (Acceptability, Tolerability, and Adherence in Randomized Trial): We will use descriptive statistics to report the number of intervention sessions attended (we expect > 80%), number of participants recruited per month (we expect 3/mo), randomization rate (number randomized/number consented; we expect about 67% of those consented will be randomized), number of assessment sessions attended (we expect > 80%), retention (number of study completers/number randomized; we expect >80%), and rate of satisfaction with treatment (total STTS-R score).

EXPLORATORY AIM

Aim 3 (To evaluate the potential efficacy of CBT-TBI for depression in the randomized pilot trial (N=40) and possible moderators and mediators of outcome):

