Hypothesis 3a: CBT-TBI will result in a greater decrease in IDS-C scores after 12 weeks (*primary outcome*) compared to waitlist control. Response over 12 weeks defined by 50% or greater decrease on IDS-C total; remission ≤ 6 on IDS-C total. Continuous variables will be analyzed by generalized mixed effect modeling, which impute missing values based on maximum likelihood estimates of missing parameters, allowing analysis of all participants. A time-by-condition interaction will be analyzed to test the intervention's efficacy. Relevant potential covariates (e.g., caregiver presence) will also be examined. The percent of responders and remitters in each group will be computed in order to estimate an effect size for the R01. Although I will test for statistical significance, the primary aim of this pilot RCT is to estimate the intervention's effect size to conduct a larger, more adequately powered R01 study, as is outlined in NIH guidelines for developing behavioral interventions¹²⁸. Given that some prior studies utilizing CBT in patients with TBI suggest large effect sizes for reducing emotional distress and depressive symptoms,^{32,34} we expect similar findings.

Hypothesis 3b: CBT-TBI will produce an increase in coping skills, adaptive thinking, positive self-appraisal, social functioning and activity level compared to waitlist control, and these factors will mediate depressive outcomes. To evaluate the indirect effect of CBT-TBI to depression (IDS-C) through coping skills, adaptive thinking, positive self-appraisal, social functioning, and activity level, we will employ an SPSS macro (PROCESS) to test the significance of the indirect effect with a bootstrapping approach to obtain confidence intervals.¹²⁹ The constructed conditional process model proposes that CBT-TBI will lead to increased coping skills, adaptive thinking, positive self-appraisal, social functioning and activity level, and that increase in these mediators will result in reduced depression. Bootstrapping is superior to other methods for determining the significance of indirect effects, as the assumption of normality for the sampling distribution is not required and power is improved.¹³⁰

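### With IDS-C scheduled only at screening and week 12, the planned time-by-condition test is a change-score comparison, usually less precise than a baseline-adjusted week-12 difference; separately, activity level has no waitlist data to support between-arm mediation

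*Protocol*

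**What the plan says.** **Efficacy.** Protocol section VI, Hypothesis 3a, and SAP Hypothesis 2a give the same plan. Continuous outcomes go into a mixed model fitted by maximum likelihood, "allowing analysis of all participants", and "A time-by-condition interaction will be analyzed" as the test of efficacy. Caregiver presence is given as an example of a covariate. Neither screening IDS-C nor the randomisation strata are named, and nothing constrains the two arms to a common screening mean. The aim is labelled exploratory, but the same paragraph says that "the primary aim of this pilot RCT is to estimate" an effect size for a larger trial.

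**Schedule.** Protocol section V, Table 1 ("Schedule of Assessments for Active CBT Patients") lists IDS-C at screening, week 12 and the 3-month follow-up, with QIDS-C at weeks 2 to 10. The schedule in Table 2 ("Schedule of Assessments for Waitlist Patients") lists IDS-C at screening and waitlist week 12, again with QIDS-C between.

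**Design.** Section IV: "randomization will be stratified by history of MDD and gender". Under section III a patient enters by meeting criteria for a major depressive episode on the MINI, or if he or she "has a total score ≥ 23 on the Inventory of Depressive Symptomatology".

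**Moderation and mediation.** The moderation model (Protocol Hypothesis 3c, SAP 2c) names only caregiver presence as a covariate and does not say whether depression is the week-12 score or the change. The mediation model (3b, SAP 2b) speaks of mediators increasing and names no screening values. It counts activity level among the mediators and predicts a rise relative to waitlist. Section V supplies the tracker only during treatment, and the waitlist schedule has no tracker row.

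**The concern.** With two visits, a time-by-condition interaction has no trajectory to estimate. It contrasts change from screening and fixes the weight on the screening score at 1, whatever the data show. A trial run to supply an effect size should not give away precision that its own screening data can recover. At stake is the width of the interval carried into the next trial, not bias in the treatment effect.

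Other models are affected too. Moderation lacks the same covariate. Mediation on change scores can turn a pre-treatment correlation between mediator and depression into an apparent indirect effect. One hypothesised mediator has no control-arm data.

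**Working it through.** **1. Number of occasions.** In the randomised period both arms have two IDS-C scores. The 3-month IDS-C belongs to treated patients and has no randomised control. QIDS-C is a different scale and is not scheduled at screening or week 12.

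**2. What the interaction estimates.** With complete data it is (week 12 minus screening, CBT) minus (week 12 minus screening, waitlist). A fitted two-visit mixed model gave -0.7963, identical to the difference in mean change. ANCOVA instead subtracts b times the screening difference, with b estimated. Its target is ρ/s, where ρ is the screening-to-week-12 correlation and s is screening SD / week-12 SD. The change score sets b = 1, so in large samples the two are equally precise only when ρ = s.

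**3. Precision.** The documents give no ρ, SDs, power calculation or allocation ratio, so there is no planned figure to reproduce. Assumed: n = 20 per arm (40 randomised, 1:1), or n = 16 (80% retention). With week-12 SD σ:

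- Var(change) = σ²(s² + 1 - 2ρs)(2/n)
- Var(ANCOVA) = σ²(1 - ρ²)(1 + 1/(2n - 4))(2/n)

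Example, n = 20, s = 1, ρ = 0.5: change SE = √(1.0 × 0.1) = 0.316σ; ANCOVA SE = √(0.75 × 1.0278 × 0.1) = 0.278σ; ratio 1.139.

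SE ratio, change score to ANCOVA:

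| n per arm | s | ρ = 0.3 | ρ = 0.5 | ρ = 0.7 |
|---|---|---|---|---|
| 20 | 1.0 | 1.223 | 1.139 | 1.070 |
| 20 | 0.8 | 1.114 | 1.044 | 0.996 |
| 20 | 0.6 | 1.034 | 0.993 | 0.996 |
| 16 | 1.0 | 1.219 | 1.135 | 1.066 |
| 16 | 0.8 | 1.109 | 1.040 | 0.992 |
| 16 | 0.6 | 1.030 | 0.989 | 0.992 |

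Simulation agreed within 0.01. With 20% of week-12 scores missing at random, the planned model against a common-baseline mixed model gave 1.173, 1.109, 1.058 (s = 1); 1.097, 1.031, 0.992 (s = 0.8); and 1.018, 0.989, 0.994 (s = 0.6).

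**4. Main effects do not repair it.** In a simulated complete data set (N = 40) the interaction was -4.284 (SE 2.90) with no covariates, with strata, with screening IDS-C, and with both. ANCOVA gave -4.877 (SE 2.68). In another set with 8 of 40 week-12 scores missing, the interaction moved only from -8.73 to -8.71 (strata) or -8.90 (screening IDS-C).

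**5. Moderation (20 per arm).** Without screening IDS-C the interaction interval is wider by 22%, 14% and 7% on change scores at s = 1, falling to 3%, -1% and 0% at s = 0.6. On week-12 scores it is wider by 3%, 14% and 38%. Once screening IDS-C is in the model, the two outcome forms give the same interaction estimate, because they differ only by a covariate already included.

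**6. Activity level.** The hypothesis needs activity in both arms over the randomised 12 weeks. The schedule provides it from week 2 in the CBT arm and not at all in the waitlist period. The arm-to-mediator path cannot be estimated. This needs no assumption.

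**7. Mediation.** Simulations used N = 40, a true mediator-to-IDS-C path of zero, and stability 0.5 (the correlation of each measure with its own screening value). With baseline mediator-depression correlations of -0.5 and -0.7 and no further week-12 correlation, the bootstrap interval excluded zero in about 8-13% of trials on change scores, against about 5% with both screening values included. At -0.3 there was little or no excess. Adding a week-12 residual correlation of -0.3 from a shared unmeasured cause gave 32-46% on change scores and 34-37% with both screening values; at -0.5 it gave 57-68% and 70%. Adjustment removes the first problem and leaves the second.

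**The case against.** The strongest reply is that both estimators are valid, that Hypothesis 3a asks about a greater decrease, which an interaction addresses directly, and that the aim is exploratory. All of that stands. A reader might infer that the planned test is biased or invalid; under randomisation it is neither, and its standard error is correct.

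The size of the loss is also assumed. Selection on the outcome scale could narrow the screening SD. Truncating screening scores at an assumed 0.5 to 1.5 SD below the mean left losses of 11-17%, 6-11% and 3-5% at pre-truncation correlations of 0.3, 0.5 and 0.7. In the table above, the loss can disappear altogether. Against that, the adjusted estimate is at worst about 1% less precise anywhere in the table.

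The effect-size route that the plan spells out is the responder and remitter percentages. That the interval for the mean difference also feeds the next trial is a fair inference from the stated purpose, but only an inference.

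On mediation, the wording about mediators increasing describes a causal chain; neither document says that change scores enter PROCESS. A reader might also infer that adding screening values makes the mediation sound. The week-12 residual-correlation results show that it does not, and the waitlist schedule has no mid-treatment mediator questionnaires that would let the mediator precede the outcome in both arms.

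**Conclusion.** The point holds as one of precision. On the scheduled data the planned efficacy term is a change-score contrast, with a standard error 7-22% larger than the adjusted estimate when the SDs are equal. The difference falls to nothing, or about 1% the other way, when the screening SD is narrow. These figures rest on assumed correlations of 0.3 to 0.7, SD ratios of 0.6 to 1.0 and 16 to 20 per arm. Because the gain is nearly free and the pilot exists to estimate an effect, the change should be made.

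The activity-level contradiction holds without assumptions. The mediation point is narrower: screening values remove only the spurious indirect effect that a baseline correlation produces when change scores are used. They do not address confounding between a mediator and IDS-C measured at the same week-12 visit.

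The documents do not show that the strata predict IDS-C, so no precision gain is claimed for them. Including them matches the randomisation.

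**What to change.** - **Efficacy** (Protocol section VI, Hypothesis 3a; SAP 2a): estimate the week-12 IDS-C difference adjusted for screening IDS-C, pre-injury MDD history and gender. Use ANCOVA, or a mixed model with a common baseline mean and strata-by-time terms. The mixed model keeps every randomised patient in the analysis, as the plan intends, though patients without a week-12 score add almost nothing to the arm contrast. Report the difference with a 95% CI beside the planned responder and remitter percentages.
- **Moderation** (Hypothesis 3c; SAP 2c): add screening IDS-C and the strata.
- **Activity level** (section II and section VI, Hypothesis 3b; SAP 2b): remove it from the between-arm hypothesis and mediation analysis, or describe it in the CBT arm only.
- **Mediation**, if run: include the screening mediator and screening IDS-C, and report indirect effects as exploratory and not causal.

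**Cost.** Wording changes in the protocol (sections II and VI) and the SAP. No new data are needed: screening IDS-C, the strata and the questionnaire mediators are already collected. The efficacy and moderation models spend three degrees of freedom each, and each mediation model two. If the strata explain nothing, the efficacy half-width at s = 1, ρ = 0.5 goes from 0.560 to 0.562 week-12 SDs, and the moderation interval widens by about 3% (4% at 32 completers).

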Galveston Orientation and Amnesia Test (GOAT)⁷⁷: A measure of orientation to place, time, and personal information used to assess post-traumatic amnesia.

Cognitive Therapy Awareness Scale (CTAS)⁷⁸: A 40-item, self-report, true-false measure of knowledge of basic CBT skills. The CTAS is a simple, brief measure that has been used in a number of studies.^{78,79,80,81} A score of 20 is suggested to be the average score obtained by individuals with no awareness of cognitive therapy.⁸²

Substance Use Questionnaire: A 15-item, self-report questionnaire that assesses if the patient used psychoactive substances in the last 30 days.

*The Alcohol Use Disorders Identification Test*: A 3-item, clinician-rated measure of alcohol consumption that can help identify individuals who are hazardous drinkers or have active alcohol use disorders.⁸³

PROMIS Pain Intensity: Measures how much a person hurts.⁸⁴

PROMIS Pain Interference: Measures consequences of pain on relevant aspects of one's life. This includes the extent to which pain hinders engagement with social, cognitive, emotional, physical, and recreational activities.⁸⁵

Depression Measures:

*Inventory of Depressive Symptomology (IDS-C30)*⁸⁶ (*primary outcome*): 30-item clinician rated scale that assesses severity of depression according to the nine DSM-IV⁵¹ symptom domains.

*Quick Inventory of Depressive Symptomatology, Clinician-Rated (QIDS-C)*⁸⁷: 16-item clinicianrated scale that assesses severity of depression according to the nine DSM-IV⁵¹ symptom domains.

Columbia-Suicide Severity Rating Scale (C-SSRS)⁸⁸: Clinician assessment of recent through lifetime suicidal ideation and behavior (i.e., attempts, interrupted and aborted attempts, preparatory behavior, and nonsuicidal self-injury).

Beck Depression Inventory II (BDI-II)⁸⁹: A 21-item self-rated questionnaire that assesses severity of depression.

Hospital Anxiety and Depression Scale (HADS)⁹⁰: A 14-item self-rated questionnaire that assesses severity of anxiety and depression.

PROMIS Bank v1.0: Depression: A 28 item, self-rated, Computerized Adaptive Test that assesses severity of depression. The first item is fixed for all participants, but participants' response will determine which item is selected next by the program; this is repeated for all subsequent items.

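### The only stated source for the R01 effect size is the responder and remitter percentages, a noisier basis than the continuous IDS-C the trial already measures and models

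*Protocol*

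**What the plan says.** Protocol section VI, Hypothesis 3a, and the SAP, Hypothesis 2a, carry the same text.

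- **Purpose.** "the primary aim of this pilot RCT is to estimate" the intervention's effect size, in order "to conduct a larger, more adequately powered R01 study". The scale of that effect size is not given.
- **Named source.** "The percent of responders and remitters in each group will be computed in order to estimate an effect size for the R01".
- **Cut-points.** "Response over 12 weeks defined by 50% or greater decrease on IDS-C total"; remission is an IDS-C total of 6 or less.
- **Continuous outcome.** The IDS-C is the primary outcome, described in Protocol section V as a "30-item clinician rated scale that assesses severity of depression". Protocol Tables 1 and 2 schedule it in both arms at screening and week 12.
- **Continuous analysis.** "Continuous variables will be analyzed by generalized mixed effect modeling", and "A time-by-condition interaction will be analyzed to test the" intervention's efficacy. No mean difference, SD, standardized effect or confidence interval from this model is named as an input to the R01.
- **Size.** Phase 4 enrols "with the goal of randomizing 40 participants" (Protocol section IV). The allocation ratio is not stated. Retention is expected to exceed 80%.

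**The concern.** The plan calls effect-size estimation the main purpose of the randomized pilot, then ties the estimate to two dichotomies of a score that will be held in full. Cutting a continuous outcome loses precision, and with 40 people there is little to spare.

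Three consequences follow. The number handed to R01 planning would be noisier than the data require. If it came from remission, it might rest on no events at all in the control arm. And because the scale is left open, three candidate effect sizes (response, remission, mean difference) would be available after the data are seen, with no prior statement of which one counts. The percentages also have no stated denominator or rule for people without a week-12 IDS-C.

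**Working it through.** The documents give no power, precision or sample-size figure for N = 40, so there is nothing of the plan's own to reproduce.

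**Inputs.** From the documents: 40 randomized; retention above 80%; response at a 50% fall; remission at 6 or less; entry by a Major Depressive Episode on the MINI or IDS-C of 23 or more. Assumed: 1:1 allocation (20 per arm, or 16 at 80% retention); normal scores; d = 0.8 for the effect the plan calls large; response of 50% versus 20%; baseline to week-12 correlation r = 0.5; for remission, week-12 SD 10 and waitlist mean 25 to 28.

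**1. Information kept by one cut** (small effect, rate p): φ(z_p)² / [p(1 − p)].

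| Rate p | Kept | Lost |
|---|---|---|
| 50% | 0.3989² / 0.25 = 0.637 | 36% |
| 20% | 0.2800² / 0.16 = 0.490 | 51% |
| 10% | 0.1755² / 0.09 = 0.342 | 66% |

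For effects from d = 0.2 to 1.2, the best possible cut still loses 34 to 36% by variance of d.

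**2. Precision of the risk difference, 50% versus 20%.** Half-width = 1.96 × √(0.25/n + 0.16/n).
- n = 20: 0.281, or 28 percentage points.
- n = 16: 0.314, or 31 points.

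**3. Precision on the d scale, 20 per arm.**
- From response rates (difference of probits): d = z(0.5) − z(0.2) = 0.84. Variance = Σ p(1 − p)/[n φ(z_p)²] = 0.0785 + 0.1021 = 0.1806. Half-width = 1.96 × 0.425 = 0.83.
- From the continuous score at d = 0.8: variance = 2/20 + 0.64/80 = 0.108. Half-width = 1.96 × 0.329 = 0.64.
- Ratio of variances: 0.108/0.1806 = 0.60, a loss of 40%.
- With baseline adjustment: 0.64 × √(1 − 0.25) = 0.56. This last step is a gain from adjustment, not from avoiding the cut.

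**4. What the planned model delivers.** With IDS-C only at screening and week 12, an unconstrained time-by-condition interaction is a difference in change. At r = 0.5 and equal SDs, the SD of change is SD × √(2 × (1 − 0.5)) = SD. So the model as written gives about 0.64. Reaching 0.56 needs ANCOVA, or baseline means constrained equal.

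**5. Remission among 20 waitlist participants.** P(none) = [1 − Φ((c − mean)/10)]²⁰.

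| Mean | c = 6 | c = 6.5 (continuity correction) |
|---|---|---|
| 25 | 56% | 52% |
| 28 | 76% | 73% |

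Fewer than one waitlist remitter is expected in every cell. With d = 0.8 the CBT-TBI arm (mean 17 to 20) expects about 1.6 to 2.9 remitters, with a 4% to 19% chance of none.

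**6. Where the loss is smaller.** Response is a fall from each person's own baseline, not a fixed cut, so it was also simulated (baseline mean 36, SD 9, truncated at 23; residual SD 11). Against a plain change score, the 50% rule lost 28 to 32% when waitlist response was 36%, and about 34 to 60% at lower rates. Against a baseline-adjusted analysis it lost 38 to 65%. Response and remission merged into one three-level outcome would lose 24 to 31% at 40 to 50% response with 5 to 15% remission.

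**The case against.** The strongest reply is that the text speaks of an effect size, not the only one, and that the planned mixed model will produce a continuous contrast in any case. That stands. A reader might infer that the plan throws the continuous information away or rules it out for the R01; the documents do not say so. What they support is narrower: the only route named is binary, and the continuous model is described only as a test.

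Other stronger readings also go beyond the documents.
- *A third is a guaranteed minimum loss.* It is a normal-theory result for one cut, and step 6 shows favourable cases below it. The plan does not merge response and remission, so the three-level case is not what it describes.
- *The estimate would rest on a handful of events.* That fits remission only. Response of 50% versus 20% gives 10 + 4 = 14 responders.
- *Everyone must fall by 74% to remit.* (23 − 6)/23 = 74% applies at a score of 23, but 23 is not a strict entry minimum, because a Major Depressive Episode on the MINI also qualifies.
- *The mixed model would rescue dropouts that the percentages lose.* With a single post-baseline IDS-C, it gains almost nothing about the effect from people missing week 12. The valid complaint is that the percentages have no missing-data rule.

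It is also fair to say that efficacy is an exploratory aim and that no efficacy conclusion changes. If the R01 were to use response as its endpoint, arm-level rates would be needed; the documents do not name that endpoint, and the fix keeps the rates.

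**Conclusion.** The point holds as a matter of precision and prior specification. Both documents name only the responder and remitter percentages as the source of the R01 effect size, while the more precise continuous contrast is available and assigned only to testing. The typical cost is about a third or more of the information. In the worked case the d-scale half-width is 0.83 rather than 0.64. Remission is the weaker of the two rates, with roughly a 52% to 76% chance of no waitlist remitter.

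These sizes rest on normality, 1:1 allocation, and assumed rates, SDs and correlation, none of which the documents give. The efficacy test itself is not affected. Nor does the change make the pilot precise: the interval stays at about ±0.56 to ±0.64 SD at full retention, and the unadjusted figure is about ±0.72 with 16 per arm.

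**What to change.** In both documents, replace the sentence on percent responders and remitters with:

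> The effect size for the R01 is the between-arm difference in week-12 IDS-C, adjusted for baseline IDS-C (ANCOVA, or the mixed model with baseline means constrained equal), reported in IDS-C points with its 95% CI and the week-12 SD by arm. If also standardized, the pooled week-12 SD is used. Percent responders and remitters are reported descriptively by arm with 95% CIs, with all randomized participants in the denominator, those missing week-12 IDS-C counted as non-responders and non-remitters, and the number missing shown.

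The week-12 SD is preferred to the baseline SD because the entry rule partly truncates baseline scores and would inflate d. As an illustration, a normal score with mean 30 and SD 10, strictly truncated at 23, has an SD of about 7.4.

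The cost is one passage of wording and a small analysis change, since the baseline-adjusted contrast is not the unconstrained interaction now planned. No new data or visits are needed.
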